11.1.4 Treatment of Overdose

BT063 has been administered to healthy subjects as IV infusions of doses up to 100 mg in 20 mL solution.

No experience with overdose of BT063 in humans exists. In case of an overdose of IMP, treatment should be suspended and the subject should receive appropriate medical treatment according to the clinical condition.

11.2 Randomization Code / Emergency Unblinding Procedures

11.2.1 Randomization

This is a double-blind study, therefore subjects, investigators, and study personnel will remain blinded with regard to the randomized treatment assignment until after database

lock. Database lock for interim analysis of study Part I will comprise data including End-of-Treatment visit (Visit 12)/Early Termination Visit of the 18th subject and all available Follow-up visit data of previous subjects.

An interactive web response system (IWRS) will be implemented and used for randomization and IMP re-supply. The randomization is thereby balanced for the entire study but not necessarily for each study site. Detailed instructions for the use of the IWRS system are provided in the IWRS User Manual that will be filed in the Investigator Site File (ISF).

11.2.2 Procedures for Unblinding

In the event of an emergency, each study site will be able to unblind subject treatment allocation via IWRS (either the Principal Investigator or a designated medic sub investigator at the study site). Unblinding shall be carried out only if a medical emergency requires the identification of the IMP for that particular subject. If possible, and time allows, investigators should make every effort to discuss the subject's case with the Sponsor or representative prior to breaking the blind. If the code is broken for a subject (via the IWRS), the Sponsor must be informed immediately. When the qualified study site personnel executes an unblind request within the system, the IWRS will prompt the requestor for information relating to the unblind request prior to releasing the code. The reason for breaking the code must be documented on the appropriate eCRF page along with the date and the system user ID of the person who broke the code.

Any subject for whom the blind is broken will be discontinued from the study.

Instructions for breaking the blind via IWRS will be described in the IWRS User Manual that will be provided to each site.

If emergency unblinding via IWRS is not possible due to a technical error or failed internet connectivity, the site must contact [REDACTED]

[REDACTED] Once the identity of the caller is authenticated, the unblinding details will be provided over the telephone.

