9 STUDY DESIGN

This is a Phase IIa, double-blind, randomized, placebo-controlled, proof-of-concept study of BT063 in subjects with SLE. Subjects between 18 and 75 years, inclusive, must have a diagnosis of SLE by American College of Rheumatology Criteria (ACR; ≥ 4 of the 11 criteria must be met for ≥ 3 months prior to screening), moderate to severe SLE disease activity demonstrated by the Systemic Lupus Erythematosus Disease Activity Index 2000 (SLEDAI-2K) of at least 6 (joint and skin component must be positive). Also, at least 5 joints with pain and signs of inflammation (66/68 joint count) or Cutaneous Lupus Erythematosus Disease Area and Sensitivity Index (CLASI) Activity score ≥ 5 must be present.

This study is divided into 2 parts. Subjects will be randomly assigned to receive BT063 or placebo in a 2:1 ratio (BT063:placebo) for both parts. Part I will enrol 18 subjects: 12 subjects to 50 mg BT063 administered by intravenous (IV) infusion 8 times and 6 subjects to matching placebo administered by IV infusion 8 times (week 0 [baseline], and then at weeks 1, 2, 4, 6, 8 10, and 12). After the last subject in Part I has completed week 14 of the study, an interim analysis of the available data (including follow up visits of previous subjects) will be performed and the DSMB will review the safety and efficacy data. Depending upon the results of that review, the DSMB will recommend that Part II be started at a higher dose of BT063 (100 mg), a lower dose of BT063 (25 mg), or at the same dose (50 mg). After reviewing the DSMB recommendation, Biotest will determine whether to continue the study and if so, which dose will be used in Part II. Part II will enrol 18 subjects: 12 subjects to BT063 administered by IV infusion 8 times and 6 subjects to matching placebo administered by IV infusion 8 times (week 0 [baseline], and then at weeks 1, 2, 4, 6, 8, 10, and 12). For both Part I and Part II, subjects will be followed for 4 months after their last dose of BT063. In both Part I and Part II, subjects will not be replaced after receiving the first dose of BT063.

Figure 9.1. Schematic of Study Design

* End of Treatment visit: 2 weeks after last drug application

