12.4 Subject Withdrawal Criteria and Procedures

In both Part I and Part II, subjects will not be replaced after receiving the first dose of BT063.

The participation of an individual subject may be discontinued prematurely for reasons such as:

- Withdrawal of written informed consent
- Required treatment with any medication known or suspected to interfere with the IMP
- Adverse reactions during administration of the IMP
- Lack of study compliance

- Treatment unblinding (see [Section 11.2.2](#))
- Any other condition which in the opinion of the investigator no longer permits safe participation in the study

A subject may discontinue participation in the clinical study at his/her own request at any time without stating a reason.

The investigator can stop a subject's participation in the study at any time if continuation could lead to disadvantages for the subject which cannot be justified by the investigator.

The reason for withdrawal of the subject must be documented by the investigator together with all data collected until the day of premature study discontinuation including laboratory results and assessment of AEs. All assessments for the End of Treatment/Early Termination Visit (Visit 12) should be performed 2 weeks after the last IMP dosing.

If a subject withdraws due to an AE or serious adverse event (SAE) please follow the instructions given in [Section 14.3.4.1](#) of this protocol.

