14.3 Adverse Events

14.3.1 Definitions

Adverse Event (AE)

Per ICH, an AE is defined as any untoward medical occurrence in a patient or clinical investigation subject administered a pharmaceutical product and which does not

necessarily have a causal relationship with this treatment. An AE can therefore be any unfavourable or unintended sign (including an abnormal laboratory finding), symptom, or disease temporally associated with the use of a medicinal (investigational) product, whether or not related to the medicinal (investigational) product. The AE may be any of the following:

- A new illness
- An exacerbation of a sign or symptom or the underlying condition or of a concomitant illness under treatment
- Unrelated to participation in the clinical study or an effect of the study medication or comparator drug
- A combination of 1 or more of the above factors

No causal relationship with the study medication is implied by the use of the term "adverse event."

Planned or elective surgical or invasive procedures for pre-existing conditions that have not worsened are not AEs. However, any complication that occurs during a planned or elective surgery is an AE. Conditions leading to unplanned surgical procedures may be AEs.

When an AE occurs after written consent has been obtained but before the first dose of study drug, the AE will be considered a non-treatment emergent AE. An AE that occurs from the time the subject receives his/her first dose of study drug until his/her last study visit will be considered a treatment-emergent AE regardless of the assessed relationship to the administration of the IMP.

For the recording of pregnancy and relevant laboratory data see [Section 14.3.2](#).

Immediately Reportable Adverse Event

Immediately reportable AEs (IRAEs) are AEs that must be reported to the Sponsor within 24 hours of the study site being informed of the IRAE (reporting requirements are detailed in [Section 14.3.2.1](#)).

Immediately reportable AEs include:

- All SAEs
- Overdose
- Pregnancy
- AEs that result in a subject's withdrawal from the study
- All AESIs ([Section 14.1.2.1](#))

Serious adverse event (SAE)

An SAE is any untoward medical occurrence or effect that at any dose:

- Results in death

- *Death is an outcome of an AE and not an AE in itself. All deaths, regardless of cause or relationship must be reported for subjects on study.*
- Is life-threatening

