14.3.2 Recording Adverse Events

Period: Subject Enrolment to the First Administration of Study Drug: Non-treatment emergent AEs will be recorded from the time when the subject is enrolled into the study (date of signature of the informed consent) until first administration of study drug.

Period: First Administration of Study Drug to Subject's last study visit: Thereafter all AEs are treatment-emergent AEs (TEAEs, see Definitions, [Section 14.3.1](#)) and will be recorded until the final follow-up visit has been performed.

Period after last study visit: Any SAE occurring after the subject's last study visit but considered by the investigator to be related to the study drug will be recorded.

If an AE (serious or not) started during the study but did not end before the final follow-up visit, the investigator should make a reasonable effort to establish the outcome and the end date. If this is not possible, the outcome recorded at the final follow-up visit will be assumed to be the final outcome.

If an event stops and later restarts, all the occurrences must be reported. Adverse events assessed as related to study medication by the investigator and all SAEs must be followed up until resolution.

Signs/symptoms should be documented if a definite diagnosis cannot be established. The investigator should attempt to establish a diagnosis of the event based on signs, symptoms and/or other clinical information. In such cases, the diagnosis should be documented as the AE and/or SAE and not the individual signs/symptoms. If a diagnosis is accompanied by unusual symptoms, the diagnosis itself and the symptoms have to be reported separately.

In addition to the definition as given, the following special types of events should be recorded:

- a) **Pregnancy** - Although not an AE per se, occurrence of pregnancy in a subject during a clinical study must be recorded.

b) **Laboratory values that are outside the normal range** and if, in the opinion of the investigator, these values represent a clinically relevant change versus pre-treatment values are also defined as AEs.

If abnormal laboratory values are signs of an AE (e.g., an infection) that has already been recorded, the respective abnormal laboratory value does not constitute a separate AE.

Wherever reasonable the reporting investigator will use the clinical term rather than the laboratory term (e.g., anaemia versus low haemoglobin value).

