The investigator will notify [REDACTED] Drug Safety department of any SAE that she or he becomes aware of and considers related to the study drug.

Following-up AEs / SAEs:

At the subject's last study visit (including the Early Termination Visit), a Safety Follow-up Visit should be scheduled up to 2 weeks after the final examination only for those subjects who experienced not resolved related AEs or laboratory parameters showing not normalized clinical relevant changes or SAEs. The assessments measured will be determined by the investigator. All data must be documented in the eCRF.

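### Breaking the blind, and possibly any early stop, can end safety observation 14 days after the last dose, although Section 9 promises 4 months

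*Protocol*

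**What the plan says.** Section 9 sets the follow-up without any exception: "For both Part I and Part II, subjects will be followed for 4 months after their last dose of BT063".

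Section 11.2.2, on emergency unblinding, says: "Any subject for whom the blind is broken will be discontinued from the study". Section 12.4 lists unblinding among several reasons under a permissive opening: "The participation of an individual subject may be discontinued prematurely for reasons such as".

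For anyone who leaves early, Section 12.4 asks the investigator to document the reason "together with all data collected until the day of premature study discontinuation including laboratory results and assessment of AEs". It then adds: "All assessments for the End of Treatment/Early Termination Visit (Visit 12) should be performed 2 weeks after the last IMP dosing". It offers no option to stop the study drug and remain under observation, and it does not mention Visit 13 or Visit 14.

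Section 14.3.4.1 accepts that the Early Termination Visit may be the last one: "At the subject's last study visit (including the Early Termination Visit), a Safety Follow-up Visit should be scheduled up to 2 weeks after". The interval is counted from that last visit. The extra visit is only for subjects with unresolved related AEs, clinically relevant laboratory changes that have not normalised, or SAEs, and the investigator chooses its assessments.

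AE collection is tied to the last visit. Section 14.3.1 defines which AEs are treatment-emergent, with the wording "An AE that occurs from the time the subject receives his/her first dose of study drug until his/her last study visit will be considered". Section 14.3.2 covers the time after it: "Any SAE occurring after the subject's last study visit but considered by the investigator to be related to the study drug will be recorded". AEs assessed as related and all SAEs are to be followed until they resolve.

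**The concern.** Safety and tolerability is the primary objective of both parts, and AE incidence from baseline to Week 14 is the primary endpoint (Sections 2 and 7). Emergency unblinding is reserved for medical emergencies, so the subjects whom Section 11.2.2 removes are those of greatest safety interest.

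An AE that leads to withdrawal is still counted, both in overall AE incidence and among AEs leading to discontinuation. What can be lost is what happens later:

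- new non-serious AEs, including non-serious AEs of special interest such as mouth ulcers;
- new SAEs judged unrelated;
- the anti-BT063, PK and safety laboratory samples planned for Visits 13 and 14.

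The protocol gives its own reason to expect late events. Section 11.1.3 reports that mouth ulcers, the only identified risk in Section 13.5.2.2, recurred 43 days after a 100 mg dose in Phase I. Immunogenicity is also a secondary objective, and it depends partly on the late samples.

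**Working it through.** **Inputs (protocol).** Doses on days 0, 7, 14, 28, 42, 56, 70 and 84; Early Termination Visit 14 days after the last dose (Section 12.4); conditional safety visit up to 14 days after that (14.3.4.1); Visit 14 on day 196 (13.1.14); primary window to Week 14, day 98 (Section 2); mean half-life 20 to 26 days (11.1.3).

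**The plan's own figure.** For a completer, day 196 − day 84 = 112 days = 16.0 weeks. This agrees with the 16 weeks of follow-up in Section 13.2, and 4 + 12 + 16 = 32 weeks agrees with its total. The promise in Section 9 is thus met by the schedule for completers.

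**Observation after the last dose for an early stopper.**

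- Early Termination Visit as last visit: 14 days. Lost: 112 − 14 = 98 days.
- With the conditional safety visit: 14 + 14 = 28 days. Lost: 112 − 28 = 84 days.
- A new non-serious event 43 days after the last dose falls beyond both limits.

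**Drug remaining**, as 2^(−t/h) with h = 20 and 26 days, assuming mono-exponential decline:

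| Days after last dose | h = 20 | h = 26 |
|---|---|---|
| 14 | 61.6% | 68.9% |
| 28 | 37.9% | 47.4% |
| 43 | 22.5% | 31.8% |
| 112 | 2.1% | 5.0% |

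**Primary-window days lost** for a last dose on day d: max(0, 98 − (d + 14)), or max(0, 98 − (d + 28)) with the conditional visit.

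| Last dose, day | Lost | Lost with conditional visit |
|---|---|---|
| 0 | 84 | 70 |
| 7 | 77 | 63 |
| 14 | 70 | 56 |
| 28 | 56 | 42 |
| 42 | 42 | 28 |
| 56 | 28 | 14 |
| 70 | 14 | 0 |
| 84 | 0 | 0 |

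**Weight of one subject.** Each part has 12 active and 6 placebo subjects, not replaced once dosed: 1/12 = 8.3% and 1/6 = 16.7% of an arm.

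**Fit of Visits 13 and 14.** They are fixed at days 140 and 196. For a last dose on day 84, 84 + 112 = day 196, which is Visit 14. For a last dose on day 14, 14 + 112 = day 126, which matches neither visit.

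**The case against.** Only the unblinding rule is explicit. For other early stoppers, nothing cancels Visits 13 and 14, and the reading that they leave rests largely on one parenthesis in Section 14.3.4.1. Section 14.3.2 also says that AEs are recorded until the final follow-up visit has taken place, which could mean that collection continues. Section 9 may be read as the general plan and Sections 11.2.2 and 12.4 as specific rules for leaving early. An emergency that justifies unblinding would often be an SAE. It would then be followed to resolution and qualify for the extra visit, so 28 days would be the fairer figure. Much of the 98-day loss lies after Week 14, the residual-drug figures come from single doses in healthy subjects, and the day-43 case is a recurrence in one subject.

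Part of this stands. For subjects who are not unblinded, early exit is allowed by the text but not ordered. The permissive wording of Section 12.4 against the mandatory wording of Section 11.2.2 is a minor point, because Section 12.4 cross-refers to 11.2.2. The percentages describe remaining exposure and do not count missed events.

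The rest does not remove the problem. The sentence in Section 14.3.2 belongs to a period whose label ends at the subject's last study visit. Following an SAE that is already open does not capture a new non-serious AE, a new SAE judged unrelated, or the missing samples. A specific rule that overrides the promise in Section 9 still breaks that promise.

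**Conclusion.** The concern holds and should be fixed. For subjects whose blind is broken, Sections 9 and 11.2.2 conflict as written. For other early stoppers, the protocol does not require the promised follow-up and allows the last visit to fall 14 days after the last dose.

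Up to 98 of 112 days of post-dose observation can be lost, or about 84 with the conditional visit. The loss within the primary window runs from none (last dose on day 84) to 84 days (last dose on day 0). The day counts assume nominal visit days. The residual-drug figures also assume mono-exponential decline at the Phase I half-lives. The protocol states no expected number of early stoppers, so neither the number of subjects affected nor the number of events missed can be given.

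**What to change.** Reconcile Sections 11.2.2, 12.4 and 14.3.4.1 with Section 9, and make the AE collection periods in 14.3.1 and 14.3.2 match:

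- Separate stopping treatment from leaving observation. State whether breaking the blind ends only the former, and use the same wording in 11.2.2 and 12.4.
- Unless consent is withdrawn, complete the 4 months of post-dose safety follow-up that Section 9 already promises: AEs including those of special interest, anti-BT063 antibodies, PK and safety laboratory.
- State how Visits 13 and 14 apply after an early stop, whether at fixed study days or counted from the last dose.
- Keep these data in the safety set, which already includes everyone dosed, and flag data collected after unblinding.

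The cost is protocol wording and up to two visits for each early stopper, using assessments already designed for Visits 13 and 14. No rule on when the study drug is stopped is proposed.

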11.3 Drug Accountability

The investigator or his/her designee must maintain records to document adequately that the subjects were provided the IMP as specified in the protocol and to reconcile all IMPs received for the study. The investigator must ensure that consignments of IMP are received, and that the IMP is safely and appropriately handled and stored.

Drug re-supply will be managed by the IWRS system.

The investigator or designee must keep sufficient documentation of the delivery, use, and destruction or return of unused, used, or partially used packages of IMP. The documentation must include dates, quantities, subject numbers, batch numbers or other identification numbers, and expiry dates.

After drug accountability procedures are complete, used and unused IMPs are to be destroyed at the site in accordance with local procedures, or returned to the Sponsor or its representative for destruction.

The investigator must allow the Clinical Research Monitor (monitor) to perform drug reconciliation. The entries in the eCRF as well as the documentation kept in the ISF will

be compared with the returned and residual IMPs, with clarification of any discrepancies or inconsistencies.

11.4 Previous and Concomitant Medication or Treatment

Subjects should be on stable doses of concomitant medication for SLE activity maintenance and symptom control (e.g., azathioprine, methotrexate, leflunomide, mycophenolate mofetil, cyclosporine, antimalarials such as chloroquine or hydroxychloroquine, steroids, NSAIDS/pain medication), without change in the type or dose of the drug used during the 8 weeks prior to baseline (for steroids and NSAIDs/pain medication 2 weeks) with the expectation that there will be no need for change in concomitant medication until the End of Treatment visit (ideally throughout the whole study); however, if the subject is taking an oral glucocorticosteroid at a dose higher than equivalent to 20 mg prednisone/day, and planning to reduce the dose of glucocorticosteroid, the dose can be titrated during the screening period so that the subject has been on at most, a 20 mg/day dose of 2 weeks by day 0 (baseline; i.e., first BT063 dose).

Concomitant medications should not exceed the doses outlined in the summary of product characteristics (SPC) or standards for SLE management; except for oral glucocorticosteroids which are limited to a dose equivalent to 20 mg prednisone/day.

All previous and concomitant medications will be recorded in the appropriate sections of the eCRF.

11.5 Prohibited Medication or Treatment

Medication other than allowed SLE treatments that is considered necessary for the subject's safety and well-being may be given at the discretion of the investigator and recorded in the appropriate sections of the eCRF. Investigators are encouraged to discuss the introduction of any restricted medications with the Sponsor or its representative.

Medications that are restricted or have special allowances during the study are listed in [Table 11.1](#). These restrictions begin at screening and are to be followed through the End of Treatment Visit at W14. During the 14-week follow-up period, certain medications may be administered at the investigator's discretion. However, no new medications for SLE should be started at any time during the study.

Table 11.1: Treatment Restrictions

Treatment	Restriction or Allowance
Glucocorticosteroids:	
Oral Glucocorticosteroids: stable dose \leq 20.0 mg prednisone daily or equivalent for at least 2 weeks prior to baseline and through the End of Treatment Visit at week 14. At most two short courses of an increased dose of oral glucocorticosteroids (i.e., 5 days) are allowed between week 4 and week 12 for management of flares. During the follow-up period these medications may be administered at the investigators discretion.
 
Intramuscular or intra-articular Glucocorticosteroids: not permitted in the 4 weeks prior to screening and during the entire study. If necessary, 1 intra-articular steroid injection is allowed, but the treated joints cannot be assessed within 4 weeks.
 
Intravenous Glucocorticosteroids (pulse therapy): not allowed within the 6 months before screening and during the entire study.
 
Inhaled and topical Glucocorticosteroids: use of topical steroids is allowed, but not within 24 hours before assessment.

Antimalarial drugs: hydroxychloroquine/ chloroquine	Stable dose levels up to the highest dose defined by the SPC for treatment of SLE are allowed during the 8 weeks prior to baseline and through the End of Treatment Visit at week 14. During the follow-up period these medications may be administered at the investigators discretion.
Immunosuppressive drugs: azathioprine, methotrexate, leflunomide, cyclophosphamide (oral), mycophenolate mofetil, cyclosporine	
Stable dose levels up to the highest dose defined by the SPC for treatment of SLE are allowed during 8 weeks prior to baseline and through the End of Treatment Visit at week 14. During the follow-up period these medications may be administered at the investigators discretion.
 
Intravenous cyclophosphamide is not allowed within the 6 months before screening and during the entire study.

Biological therapies: Rituximab, Belimumab	
Rituximab is not allowed within the last 48 weeks before screening and during the entire study.
 
Belimumab is not allowed within the last 12 weeks before screening and during the entire study.

Non-steroidal treatments:	
Non-steroidal topical treatments of skin lesions are allowed; however, not within 24 hours before assessments.
 
Stable dose levels of the following NSAIDs and -Coxibs are allowed up to the maximum daily doses stated during the 2 weeks prior to baseline and through the End of Treatment Visit at week 14; however, not within 24 hours before assessments: diclofenac (150 mg); ibuprofen (2400 mg), naproxen (750 mg), meloxicam (15 mg), etoricoxib (90 mg), celecoxib (200 mg).
 
During the follow-up period these medications may be administered at the investigators discretion.

'Rescue' pain/analgesic treatment on demand:	
Paracetamol/acetaminophen: can be taken during the study up to a maximum of 4000 mg per day; maximum 2000 mg per day on the day before joint assessment. Not to be taken within 12 hours prior

Treatment	Restriction or Allowance
	to joint assessment.
Folic acid:	Folic or folinic acid supplementation may be administered at the discretion of the investigator and in accordance with any local guidelines. If applicable, dose should remain stable from ≥ 8 weeks prior to baseline and where possible, throughout the entire study.
Vaccinations:	Any vaccination within 8 weeks prior to screening and throughout the entire study is not allowed, except for influenza and a tetanus booster.
Anti-retrovirals:	Anti-retroviral therapy is prohibited throughout the entire duration of the study.
Antibiotic or antiviral therapy:	Subjects who have infections requiring antibiotic or antiviral therapy (by any route of administration) in the 2 weeks prior to baseline are not eligible for the study. IV antibiotics are not allowed during the entire study, however oral antibiotics are allowed.
Investigational agents:	Subjects cannot have received any investigational agent within 90 days or within 5 half-lives of the investigated compound, whichever is longer, prior to baseline and during the entire study.
Plasmapheresis, IVIg	Plasmapheresis and or IVIg therapy are not allowed during the entire study; IVIg is not allowed within 12 weeks before screening.
Others:	All other medications including over-the-counter self-administered medications, herbal remedies and traditional medicines (including single doses) administered in the 6 weeks prior to screening and during the study period are to be recorded in the source documents and the eCRF. Doses, route of applications, duration of treatment, and reasons for prescription are also to be recorded.

